**Intervention Study
Protocol**

A Mind-Body Intervention to reduce symptoms among people aging with HIV (NCT03840525)

Principal Investigator: [name]., Associate Professor, Florida International University

Supported by:
The National Center for Complementary and Integrative Health

Tool Revision History

Version Number:3.0

Version Date: June 25, 2019

Summary of Revisions Made: Added more details for recruitment and screening, and all assessment interviews

Version Number:4.0

Version Date: September 2, 2019

Summary of Revisions Made: Removed staff ([name], [name]) and added new ones.

Version Number: 5.0

Version Date: November 20, 2019

Summary of Revisions Made: Added new compensation for group attendance as well as transportation (Uber Health); as well as personnel changes.

Version Number: 6.0

Version Date: January 17, 2024

Summary of Revisions Made: Removed Draft watermark; updated sample size from 72 to 48 (as approved by NIH); updated study design flowchart to reflect final sample; updated inclusion criteria to include reliable internet access; and procedures updated to reflect remote delivery changes due to covid-19.

Version Number 7.0

Version Date: March 5, 2024

Summary of Revisions Made: updated the list of investigators by adding [name]; added a note regarding the remote delivery of the intervention due to covid-19 in the Precis section.; removed duplicate objectives.

TABLE OF CONTENTS

	Page
FULL PROTOCOL TITLE	1
Tool Revision History	3
TABLE OF CONTENTS	4
STUDY TEAM ROSTER	6
PARTICIPATING STUDY SITES	6
PRÉCIS	6
1. STUDY OBJECTIVES	7
2. BACKGROUND AND RATIONALE	8
2.1 Background on Condition, Disease, or Other Primary Study Focus	8
2.2 Study Rationale	8
3. STUDY DESIGN	9
4. SELECTION AND ENROLLMENT OF PARTICIPANTS	11
4.1 Inclusion Criteria	11
4.2 Exclusion Criteria	12
4.3 Study Enrollment Procedures	12
5. STUDY INTERVENTIONS	12
5.1 Interventions, Administration, and Duration	12
5.2 Handling of Study Interventions	13
5.3 Concomitant Interventions	13
5.4 Adherence Assessment	13
6. STUDY PROCEDURES	16
6.1 Schedule of Evaluations	16
6.2 Description of Evaluations	19
6.2.1 Screening Evaluation	19
6.2.2 Enrollment, Baseline, and/or Randomization	19
6.2.3 Blinding	21
6.2.4 Followup Visits	21
6.2.5 Completion/Final Evaluation	21

1. STUDY OBJECTIVES

The **specific aims** for the proposed study are as follows:

Aim 1: Refine and culturally adapt a TCQ intervention protocol for a diverse sample of older PWH by conducting an expert panel (n=3), key informant interviews (n=10), a ‘dry run’ intervention (n=10), and 2 focus groups (n=10).

Hypothesis 1: The TCQ intervention content, recruitment process, and adherence strategies will be determined to be culturally appropriate for a diverse sample of older PWH.

Aim 2: Evaluate the acceptability of the TCQ intervention protocol for older PWH every week, 2-week post-intervention, and 3 months follow up (n = 48).

Hypothesis 2a: TCQ intervention sessions, home practice sessions, control condition, and adherence strategies (weekly phone call, newsletter, buddy system) will be rated acceptable among older PWH (> 80%).

Hypothesis 2b: TCQ intervention and control conditions will have high acceptability (%) recruited who enroll; % who attend all sessions; % who regularly do home practice sessions; % complete follow up) among older PWH.

Aim 3: Evaluate the feasibility of the TCQ intervention protocol for older PWH every week, 2-week post-intervention, and 3 month follow up (n = 48).

Hypothesis 3a: Participants in the TCQ intervention will report use of the TCQ practice at 3 months follow up (>80%).

Hypothesis 3b: Trainers will report high feasibility of the TCQ intervention with clinic infrastructure and participant abilities (>80%).

Hypothesis 3c: Trainers will show high intervention fidelity (>90%) as measured by the Intervention Fidelity Checklist.

The clinical trial will aim to address AIM 2 and 3.

Design and Outcomes

This is an exploratory clinical trial in which participants will be randomized into 3 conditions: a tai chi/qigong intervention condition, a ‘sham’ qigong attention-control condition, and a standard of care group. The trial is to test the acceptability and feasibility of both the intervention and the appropriateness of the control condition (primary outcomes). Assessments will be conducted at baseline, 2-week post intervention, and 3 months follow up. Measures include demographics, psychological and physical symptoms, acceptability, feasibility, and intervention fidelity measures. Psychological and physical health are secondary outcomes.

Interventions and Duration

Both the intervention (qigong) condition and the sham qigong control condition will last 12 weeks in duration. The third arm will be a standard of care wait-list control condition which receives nothing. In addition, participants will be asked to do a follow up assessment within 2 weeks of completing the intervention; and again 3-month post intervention. In total, study participation should be approximately 6 months.

Sample Size and Population

The target population will be individuals living with HIV who are 50 years of age or older. The trial will enroll and randomize 48 participants into either the intervention or control conditions. Randomization procedures were determined by our data analyst and biostatistician; and is described in further detail below.

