5.4 Adherence Assessment

Satisfaction surveys will be administered to each participant in the TCQ and in the SQG groups to assess adherence to the intervention (or control) group. Surveys will ask about their satisfaction with the groups, trainer, intervention content, home practice, video, the in-class 'buddy', and newsletter. Surveys will be administered before and after each session. The survey before each session will ask about the previous group they attended, and the survey administered after each session will assess satisfaction about that class.

Because acceptability and feasibility are the primary outcomes of the study, specific benchmarks were identified and approved by NCCIH to determine acceptability and feasibility. These are listed in the table below.

Table 2. Acceptability and Feasibility Benchmarks and Assessments

Aspects of Acceptability being Measured (adapted from Sekhon, et al (2017)[49])	Definition	Benchmark
Burden	Discontinuation/non-attendance	< 20% of TCQ and the sham qigong condition will drop out at 3 months follow up
Ethical Consequences	Any side effects with intervention	< 10% of participants will report any physical soreness or difficulties in doing qigong
Experience	Participant's experience and satisfaction	>80% qigong participants will perceive intervention positively >80% qigong participants will rate it very satisfactory or satisfactory
Affective Attitudes	Participants attitudes toward the intervention	>80% of participant in qigong condition will report positive attitudes about it (very good/good)
Opportunity Costs	Adherence and participation	Participants in both qigong and sham conditions will attend at least 75% of all sessions. Participants in the qigong condition will adhere to home practice at least 75% of the time expected (i.e., 112 out of 150 minutes/week)
Intentions	Willingness to participate	>80% qigong participants would be willing to participate again >80% qigong participants intend to continue qigong practice
Aspects of Feasibility being Measured (adapted from Bowen, et al., 2009 [50])	Definition	Benchmark
Demand	Likelihood that intervention will be used	>80% of qigong participants will report any qigong practice in the past week
Implementation	Can the intervention be implemented in a setting, often a real-world setting	Trainers will execute intervention >80% of the time >80% of trainers will rate resources needed to implement as very good/good

		>80% of trainers will report positive effects on population

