6. STUDY PROCEDURES

Table 2. Measures and time of administration

Assessments	# of items/alpha	Screen	Baseline	Weekly/During Intervention	Post Intervention	3 month Follow up
Eligibility Age, HIV status (self-report/lab test) Any mind-body practice in past 12 months GAIN Cognitive Impairment Can stand up for 10 min	6-items	X X X X				
Demographics and Covariates^{85,86} HIV related stigma Social Support Scale DAST AUDIT	6-items/ $\alpha = .75$		X X		X X	X X
Psychological Symptoms^{87,88} Depression Anxiety & Stress Scale (DASS-21)	21 items/		X		X	X
Physical Symptoms^{89,90} The Revised Sign & Symptom Checklist for HIV (Holzemer) HIV-related Fatigue Scale (MAF)	45 items; $\alpha = .71 - .91$		X X		X X	X X
Adherence⁹¹ 5-item Adherence questions MMAS-8 Viral load (from participants)			X X		X X	X X
Feasibility # approached (if face-to-face) # screened # eligible # consented and enrolled		X X X X			X X X X	

# refused to participate Reasons for refusal # randomized into study % attended TCQ and control sessions % completed home practice % completed FU assessments		X X X			X X	X X	X
Acceptability Satisfaction surveys per session Satisfaction with adherence strategies (weekly calls, buddy system, etc)				X	X		
Feasibility of implementation in clinic setting (trainers)					X		
Intervention Fidelity Meditative Movement Inventory (participants) Intervention Fidelity Checklist	9 items; $\alpha = .86-.90$			X	X		

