Similar data analysis will be conducted for both acceptability and feasibility. To address acceptability among participants, we will use data from the satisfaction survey which will be administered weekly during the intervention and at post-intervention. Individual items from the survey such as percent sessions attended, frequency of home practice sessions, average length of home practice sessions, and questions on opinion of the intervention sessions, home practice sessions, and video, will be plotted over time to examine variability of acceptability measures over time. Next, participant's average score over the intervention period will be averaged. These averages, as well as the items from the post-intervention satisfaction survey will be categorized into acceptable, borderline acceptable, or not acceptable. Cutoffs will be based on the approved benchmarks. From these data we will determine the proportion of participants who rate the intervention as acceptable. To estimate precision, 95%CI will be calculated using Wilson's score method, which uses asymptotic variance and is appropriate for small sample sizes¹⁰⁰. If the proportion of participants who rate the intervention as acceptable is 80% or greater, we will consider the intervention acceptable. If it is not, we will evaluate the width of the confidence interval to determine variability, as well as look specifically at each item to determine what aspects are deemed unacceptable. Feasibility will be measured by assessing the study retention rate, whether it is feasible for participants to do the movements, and whether it is feasible to deliver the intervention remotely.

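### Hypothesis 2a's >80% for the control condition and adherence strategies has no pass rule in section 9.1 and no rating benchmark in section 5.4; the inequality and the clinic-fit item also need aligning

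*Combined protocol and SAP*

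**What the plan says.** **Hypothesis and primary outcome.** Section 1, Hypothesis 2a, lists the TCQ sessions and then "home practice sessions, control condition, and adherence strategies (weekly phone call, newsletter, buddy system) will be rated acceptable among older PWH (> 80" per cent). Design and Outcomes in the same section adds: "The trial is to test the acceptability and feasibility of both the intervention and the appropriateness of the control condition (primary outcomes").

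**Benchmarks.** Table 2 in section 5.4 holds the benchmarks approved by NCCIH. Its satisfaction row reads ">80% qigong participants will rate it very satisfactory or satisfactory". The other participant ratings set at >80% (perception, attitudes, willingness, intention) are likewise worded for qigong participants or the qigong condition. Sham appears in two rows: "< 20% of TCQ and the sham qigong condition will drop out at 3 months follow up" and "Participants in both qigong and sham conditions will attend at least 75% of all sessions". No row covers the phone calls, newsletter or buddy system.

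**Data.** Section 5.4 states: "Satisfaction surveys will be administered to each participant in the TCQ and in the SQG groups". The content of those surveys includes the buddy and the newsletter. The schedule of measures in section 6 lists "Satisfaction with adherence strategies (weekly calls, buddy system, etc").

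**Analysis.** Section 9.1 sorts each participant's averages and items into acceptable, borderline or not acceptable, and says "Cutoffs will be based on the approved benchmarks". It then calls the intervention acceptable if the proportion of participants rating it so is at least 80%. It names no rule for the control condition or the adherence strategies.

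**Delivery.** The Précis and section 3 describe remote delivery by Zoom, and section 9.1 names feasibility of remote delivery as something to be measured. Hypothesis 3b and the Integration row of Table 2 still ask trainers about clinic infrastructure, and the trainer item in the section 6 schedule refers to the clinic setting.

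**The concern.** A three-arm pilot with a sham arm has to settle whether that sham is fit to carry into a larger trial. Section 1 treats this as primary and gives it a number. The analysis section and the benchmark table do not carry that number across to the sham or to the adherence strategies. An analyst working from sections 5.4 and 9.1 would report sham dropout and attendance against benchmarks, but would have no instruction to judge sham satisfaction, or the calls, newsletter and buddy system, against >80%. The choice would then be made after the ratings are seen.

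Two smaller matters affect the same decision rules. A result of exactly 80% is a pass in section 9.1 and a failure in section 1 and Table 2. And the Integration benchmark would describe fit with a setting in which sessions are no longer held.

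**Working it through.** The plan derives no figure on this point, so there is none to reproduce. The check is a comparison of text followed by counts.

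**1. Where the >80% rating applies**

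| Object rated | Hypothesis 2a | Table 2 (5.4) rating row | 9.1 pass rule | Rating collected |
|---|---|---|---|---|
| TCQ | >80% | yes, >80% | yes, at least 80% | yes |
| Control (sham) | >80% | none (dropout and attendance only) | none | yes (5.4) |
| Adherence strategies | >80% | none | none | yes (5.4, 6) |

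Table 2 names qigong and sham together when it means both, so its qigong-only rows cannot be read as covering sham.

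**2. What >80% means in counts.** Equal allocation gives 48/3 = 16 per arm. Section 9.1 prints 24 per arm, but 3 × 24 = 72, not 48, so both sizes are shown. The smallest k with k/n > 0.80, and the Wilson interval named in section 9.1, [p + z²/2n ± z√(p(1−p)/n + z²/4n²)] / (1 + z²/n) with z = 1.96:

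- Sham, n = 16: k = 13, p = 0.8125. Centre (0.8125 + 0.1200)/1.2401 = 0.752; half-width 1.96 × √(0.00952 + 0.00375)/1.2401 = 0.182. CI 57.0% to 93.4%.
- Sham, n = 24: k = 20 (83.3%), CI 64.1% to 93.3%.
- Adherence strategies rated by TCQ and sham together, n = 32: k = 26 (81.3%), CI 64.7% to 91.1%.

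**3. What the two sham rows leave open (illustration, n = 16).** Dropout below 20% allows 3/16 = 18.8%. Sessions number 2 × 2 + 10 × 1 = 14, and 75% of 14 is 10.5, so 11/14 = 78.6% meets the attendance row. Both rows could be met with 8/16 satisfied (50%, CI 28.0% to 72.0%), against the 13/16 that Hypothesis 2a needs. Neither Table 2 nor section 9.1 says how that shortfall is to be judged.

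**4. The two inequalities.** They give different counts only if 0.8n is a whole number, that is, if n is a multiple of 5.

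| n | needed for >80% | needed for at least 80% |
|---|---|---|
| 15 | 13 | 12 |
| 16 | 13 | 13 |
| 20 | 17 | 16 |
| 24 | 20 | 20 |

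One missing rating from 16 leaves n = 15, and 12/15 = 80.0% (CI 54.8% to 93.0%) then passes section 9.1 and fails Hypothesis 2a.

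**5. Trainer denominator.** The roster has two trainer entries. Section 5.1 plans 3 to 4 TCQ instructors, and separately 1 to 2 sham facilitators plus the research coordinator. One dissent gives 1/2 = 50%, 2/3 = 67% or 3/4 = 75% if only TCQ trainers count, but 5/6 = 83% or 6/7 = 86% if sham staff are included. Whether one dissent fails the benchmark therefore depends on an unstated denominator.

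**The case against.** The best reply is that the threshold is not missing at all. Hypothesis 2a prints it and the surveys collect the ratings. The cut-off sentence in section 9.1 most naturally sets participant-level categories (for example, what counts as a satisfied respondent), and the 80% proportion rule follows separately. Sections 5.2 and 6.2.3 even speak of a sham intervention, so the rule might be stretched to cover it. Analyses are declared primarily descriptive, and a result below 80% leads to a look at interval width and individual items, not to stopping. Clinic fit also remains meaningful: the two community sites are still listed and clinic staff still recruit.

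Much of this stands, and it limits the point to a rule that needs one explicit extension. It does not remove the point: the rule as written reaches a single conclusion about the intervention, under aims stated for the TCQ protocol. Keeping a clinic-fit question is reasonable, but it does not measure fit with remote delivery.

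Three stronger readings are tempting, and the documents do not support them:

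- That the plan gives opposite answers about the control. Meeting dropout and attendance while failing satisfaction is a mixed profile across separate aspects of acceptability. No passage says that meeting those two rows makes the sham acceptable.
- That the trainer criterion should become unanimity. That follows by arithmetic only for 2 to 4 trainers, and the denominator is not settled.
- That the lack of a fidelity row in Table 2 is an error. Fidelity is listed as a separate kind of measure, and Hypothesis 3c already gives its >90% and its instrument. The row on trainers executing the intervention more than 80% of the time may measure something else.

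**Conclusion.** The concern holds in limited form. A numerical criterion attached to a primary outcome is not carried into the analysis rule or the benchmark table for two of the things it covers, the control condition and the adherence strategies. This rests on one assumption: that the control condition in Hypothesis 2a means the sham arm, because only TCQ and sham participants are surveyed.

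The inequality mismatch is real but narrow. It has no effect at 16 or 24 rated and matters only at multiples of 5. The clinic-fit point is a conflict between the trainer item and the remote design, not between hypothesis and table, since Hypothesis 3b and the Integration row agree with each other. None of this undermines the trial, but it should be settled because it determines how primary outcomes are declared met.

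**What to change.** 1. In section 9.1, state that >80% applies to the sham arm's satisfaction ratings and to the adherence-strategy ratings as well as to TCQ. Report each as k/n with a Wilson 95% CI, and say that the control condition means the sham arm.
2. Use one inequality throughout. Hypothesis 2a and Table 2 already use >80%, so only section 9.1 changes.
3. Have the trainer Integration item ask about fit with remote delivery, with the clinic-fit item kept alongside if wanted, and align Hypothesis 3b and the section 6 schedule.
4. Report trainer results as k of n, stating who is in the denominator.

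The cost is wording and one trainer item, with no new participant data. NCCIH must agree to any change in the benchmarks it approved.

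The Version 6.0 entry in the revision history refers to a final sample, so enrolment may be complete. If data collection is finished, keep the approved benchmarks as they are and apply Hypothesis 2a's already stated >80% to the sham and adherence-strategy ratings. Label any addition to Table 2 post hoc, and note as a limitation that Integration was rated against the clinic setting.

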2. BACKGROUND AND RATIONALE

2.1. Background on Condition, Disease, or Other Primary Study Focus

Half of those infected with HIV in the United States are over 50¹, and this will increase to 70% by 2020². Although death rates have decreased for all age groups, it has increased for older adults aged 60 and older. Over 60% of those HIV+ and over 50 are racial/ethnic minorities¹. Older people living with HIV/AIDS (PWH) report a myriad of psychological and physical symptoms, more than do their younger HIV+ counterparts³. More symptoms lead to poorer medication adherence⁴ and higher viral load. Few interventions exist for older PWH⁵; only 2 interventions on reducing depression and increasing coping symptoms^{6,7}. None addressed physical symptoms.

Mind-body interventions, like Tai chi and Qigong (TCQ) improves both physical and psychological health and might promote immune functioning⁸. TCQ is a series of slow, low-impact meditative movements that integrates breath work, meditation, and stances. Using the National Center on Complementary and Integrative Health (NCCIH) *Framework for Developing and Testing Mind and Body Interventions*, we propose the refinement, acceptability and feasibility testing of a standardized mind body intervention – Tai Chi/Qigong Easy – shown efficacious with cancer patients, with an ethnically diverse population of older PWH (50 years of age or older). Participants will be recruited from Borinquen Health Clinic, a federally qualified health center in Miami, Florida. The intervention will be adapted to fit the cultural and HIV context; then participants will be randomly assigned to either a TCQ intervention, a sham Qigong (SQG) control condition, or a standard of care group.

2.2. Study Rationale

Co-investigator, [name], has conducted extensive research on qi gong interventions trying to alleviate fatigue and other symptoms among breast cancer survivors. In an NCCAM funded pilot study (U01 AT002706-03: PI [name]), 101 breast cancer survivors (BCSs) were randomized to a 12-week Qigong/Tai Chi Easy (TCQ) intervention or sham Qigong (SQG) using similar, gentle movements without meditative state/breath focus) (publication accepted to Annals of Behavioral Medicine). Pre- and post-intervention data were collected for 87 women, mean age, 58.8,

completing the intervention (15% attrition) on the primary outcome, *fatigue*, and several other symptom and mood related factors. Fatigue was significantly decreased for TCQ compared to SQG ($p = 0.013$). The estimated effect size (Cohen's D) was 0.56, suggesting a "medium" effect, which is remarkable when one considers that the comparison group was confirmed to have the *same level of exertion and was perceived as equally beneficial*. Other symptoms/mood factors (depression, sleep quality, cognitive function) significantly improved from pre-to-post TCQ intervention (with higher values but not significantly more than the SQG intervention) indicating small effect sizes for these symptoms ranging from .19-.31. In another study, dissemination of TCQ through community sites⁹³ was demonstrated through a successful "**practice leader**" **training** model where the **Tai Chi Easy form was formalized, manualized, and standardized** for implementation across the US (18 sites). A significant decrease in stress was found pre- to post-intervention using the Perceived Stress Scale (PSS)⁹⁴: PSS scores (10 items, alpha = .88) decreased from 1.28 to 1.20 with 4 indicating higher stress on a scale of 0-4, ($t = 3.03$, df 299, $p = .03$).

Individuals living with HIV suffer from multiple psychological and physical symptoms. [name] is currently collecting data on a cohort of HIV+ individuals at multiple sites in Florida. Preliminary data analysis shows that the older PWH in this cohort is experiencing both physical and psychological symptoms: 26% severe anxiety; 29% severe depression; and 22% had physical health problems. However, 45% of those over 50 reported that physical health problems did not limit their physical activities, which suggest that a mind body intervention is feasible physically.

[figure not shown]
